10.2. Fast Desaturation**10.2.1. Sample Size**

10.2.1.1. This study will include at least 10 Dark skin pigmentation subjects based on ISO-80601-2-61.

10.2.1.2. This study will include at least 10 Light skin pigmentation subjects based on ISO-80601-2-61.

10.2.2. Exclusion Criteria

10.2.2.1. Reference device malfunction and/or provides inconsistent SpO_2 value.

10.2.2.2. Data corruption by device failure or data communication problems.

10.2.2.3. Low signal quality, e.g. due to noise or interference.

10.2.2.4. Subject without valid fast desaturation event of 92% or lower reference SpO_2 .

10.2.3. Detection Rate of Fast Desaturation Events:

$$Detection\ Rate = (Nt / N_{desat}) \times 100\ (%)$$

Where, Nt = Number of Detected Event by Test Device

N_{desat} = Number of All Valid Fast Desaturation Events by Reference SpO_2

Detection Rate will be calculated for overall and each desaturation sequence (Condition B-1~3)

10.2.4. No Read Rate for Spot Checks:

$$No\ Read\ Rate = (Nf / N_{spotcheck}) \times 100\ (%)$$

Where, Nf = Number of Spot Checks without Valid SpO_2

$N_{spotcheck}$ = Number of All Spot Checks using Apple Watch

No Read Rate will be calculated for overall and each desaturation sequence (Condition B-1~3)

11. DATA MANAGEMENT**11.1. Data Management and Confidentiality**

All documents associated with this protocol will be securely stored in a physical location or on password-protected computers. The confidentiality and retention of these documents will be protected to the extent provided and required by the law. All data will be de-identified before any statistical analysis. Only de-identified data will be shared with Masimo for research purposes

stated in this protocol. Data collected by the eCRF data capture software will be shared with Masimo via a secure, password-protected server that only study staff and Masimo study team members will have access to. Data will be retained for a minimum of two years following completion of the final analysis.

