3. IDENTIFICATION AND DESCRIPTION OF THE INVESTIGATIONAL DEVICE

Masimo Corporation is the developer of noninvasive technologies for the measurement and monitoring of physiological variables, such as arterial oxygen saturation (SpO₂), total hemoglobin concentration (SpHb), carboxyhemoglobin concentration (SpCO), methemoglobin concentration (SpMet), and other physiological variables to improve patient outcomes and reduce cost of care.

The Masimo W1™ is a watch that provides spot-check ECG measurements and continuous measurements of functional oxygen saturation of arterial hemoglobin (SpO₂), pulse rate (PR), and respiration rate from the pleth (RRp®). The watch has a touchscreen display, a rechargeable battery, and Bluetooth® connectivity to pair to a smartphone App.

Figure 1: Masimo W1™

Additional study devices that will be used in this study include the Apple Series 8 watch, the Masimo Rad-97 Pulse CO-Oximeter and the Masimo RD SET Adt sensor. The Rad-97 and Masimo RD SET are indicated for the continuous non-invasive monitoring of functional oxygen saturation (SpO₂), pulse rate (PR), respiratory rate (RRa), and Pleth Variability index (PVi) for adult populations.

The Apple Series 8 watch will be connected to an iPhone, results from the spot check measurements on the Apple Watch will also be manually recorded in the comments portion of a data collection software on a laptop. The Rad-97/RD SET pulse oximeter will be connected to a data collection software on a laptop.

Figure 2: Masimo Rad-97 Pulse CO-Oximeter

Figure 3: Masimo RD SET Adt Sensor

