7.4. Study Devices and Comparators

Study Devices and Technologies

- Masimo W1™ – Test
- Apple Watch Series 8 – Test
- RD SET® Adt - Control

FDA-Cleared Safety Equipment

- Capnostream 20
- Nefin bmeye
- ECG Module

Research Equipment (as needed)

- Masimo Pulse Co-Oximeter (Rad-97 or comparable)
- Data Collection Research Equipment (e.g. [REDACTED] Lab Chart, smart phone with data collection application or comparable)
- Colorimeter (e.g., Delfin SkinColorCatch or comparable)
- Warm water bottle, heating pad or Comparable
- [REDACTED]
- Laboratory CO-oximeters/blood analyzers (e.g. Radiometer ABL90 Flex or comparable)

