8.4.1.1. Condition A: Slow Desaturation

The subject may participate in a slow desaturation procedure (Condition A)

In this desaturation (Condition A) the subject will have their palms facing down. The Apple Watch Series 8 will have manual spot checks taken approximately every minute after 1 minute of each desaturation level transition and noted in Masimo data collection software.

See **Figure 4** below for an example of the spot checks distributed approximately 1 minute throughout the slow desaturation procedure.

Figure 4 Example of a Desaturation sequence for Condition A Slow Desaturation

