8.4.1.2. Condition B: Fast Desaturation

Figure 5 Example of each Desaturation sequence for Condition B Fast Desaturations

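### Detection Rate (section 10.2.3) can mix sampling opportunity with sensor performance when the continuous W1 and the spot-checked Apple Watch are compared

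*Combined protocol and SAP*

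**What the plan says.** Section 3 describes the W1 as giving "continuous measurements of functional oxygen saturation of arterial hemoglobin". For the other watch, the same section says that "results from the spot check measurements on the Apple Watch will also be manually recorded" in the data collection software. Section 7.4 labels both as test devices ("Apple Watch Series 8 – Test"), with RD SET as control. The secondary objective in section 6 compares the two watches against the reference oximeter.

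For fast desaturation, section 10.2.3 gives a single ratio. The numerator is the "Number of Detected Event by Test Device" and the denominator is the "Number of All Valid Fast Desaturation Events by Reference" SpO2. It is reported overall and for each of B-1 to B-3. A 92% reference level appears only in the subject exclusion in section 10.2.2. Section 10.2 gives no threshold, time window or sampling rule for calling an event detected by a watch.

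Section 10.2.4 adds a No Read Rate for the same sequences, with denominator "Number of All Spot Checks using Apple Watch". This confirms that spot checks are used in Condition B.

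The only check schedule in the visible text is for the slow desaturation, Condition A: "manual spot checks taken approximately every minute after 1 minute of each desaturation level transition". For Condition B, section 8.4.1.2 shows only its heading and a figure caption ("Example of each Desaturation sequence for Condition B Fast Desaturations"). Check timing and event length there are unknown to a reader of the public text and cannot be called missing from the plan.

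**The concern.** An event-level detection rate depends on two things: whether the device was read during the event, and whether the reading was low enough. For a continuous device the first is close to guaranteed. For a spot-checked device it depends on when study staff start a check and how long the event lasts. The formula in section 10.2.3 does not separate the two, and its denominator is not conditioned on an Apple check having been attempted during the event.

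No Read Rate does not close the gap. It covers attempted checks that returned no valid value. An event in which no check was attempted leaves no trace in it.

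At stake is the reading of the secondary objective in Condition B. If the W1 has the higher rate, a reader cannot tell from the planned outputs whether its sensor followed the desaturation better or whether it was simply read at the right moment.

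**Working it through.** The plan states no expected Detection Rate, hypothesis or power for this outcome, so there is no figure to reproduce. The calculation below shows how far the schedule alone could move the rate.

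**Inputs from the documents.** W1 continuous (section 3); Apple Watch spot-checked in Condition B (section 10.2.4); denominator of all valid reference events (section 10.2.3); about one check per minute in Condition A only (section 8.4.1.1).

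**Assumptions.** Check interval T, event duration D and reading window m (all in seconds) are not given for Condition B. T = 60 s is borrowed from Condition A, and nothing visible carries it over. Checks fall at random phase relative to the event. The sensor is error-free. An error-free continuous device is taken to detect every event (100%).

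**Step 1: capture by an error-free spot check.** If a reading must lie wholly inside the event,

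capture = min(1, max(0, (D − m)/T)), which is min(1, D/T) when m = 0.

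| T, m | D = 20 | D = 30 | D = 45 | D = 60 |
|---|---|---|---|---|
| 30, 0 | 20/30 = 67% | 100% | 100% | 100% |
| 60, 0 | 20/60 = 33% | 30/60 = 50% | 45/60 = 75% | 60/60 = 100% |
| 60, 15 | 5/60 = 8% | 15/60 = 25% | 30/60 = 50% | 45/60 = 75% |
| 120, 0 | 20/120 = 17% | 30/120 = 25% | 45/120 = 37.5% | 60/120 = 50% |

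A simulation of 100,000 events per setting, run for the 30, 45 and 60 s durations, agreed with the formula. The loss is zero once D is at least T + m, and total when D is no longer than m.

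**Step 2: checks timed to events.** If one check is placed inside every event, an error-free sensor reaches 100%, or 1 minus the no-read rate: 90% at an assumed 10% no reads and 70% at an assumed 30%. The schedule effect is then gone and only read failure remains.

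**Step 3: number of chances.** Even with a check in every event, a continuous device may get several chances to cross the threshold where a spot check gets one. For illustration, suppose that any reading at or below 92% counts as detection, the true value is 90%, and the error SD is 3 points.

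- One reading: Φ((92 − 90)/3) = Φ(0.667) ≈ 75%.
- Three independent readings: 1 − (1 − 0.75)³ ≈ 98%.
- Three readings with fully correlated errors: still 75%.

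Two sensors with the same error could therefore differ by 0 to about 23 points through the number of readings alone, depending on how strongly errors persist within an event.

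**Step 4: repeated events.** Section 8.4.1 lets a subject do B-1, B-2 and B-3 in one visit, so events can cluster within subjects. Section 10.1.3 adjusts precision and A_RMS for repeated measurements; section 10.2 has no counterpart and plans no interval.

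**The case against.** The strongest reply is that the effect turns on text that is not visible. Condition B may time an Apple check to each event, or its events may outlast the check interval. In either case the schedule loss in Step 1 is zero. This stands, and it rules out a reading that a reader might infer: that Detection Rate measures the sampling schedule rather than the sensor, or that two sensors with identical error would necessarily show very different rates. The documents do not establish either. The 60 s interval belongs to Condition A and the durations are assumed.

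Second, all reference events is the ordinary denominator for event sensitivity, and missing events because a watch is read intermittently can be a real as-used property. That also stands: the shared denominator is not an error. The qualification is that check timing here is partly set by study staff, so the as-used rate partly reflects study procedure.

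Third, one might say that failed Apple checks are penalised twice, in Detection Rate and in No Read Rate. This is not a defect. One rate is per event and the other per check, and nothing adds them together. It is also not stated how a failed check is scored, or whether the exclusions in section 10.2.2 for poor signal or communication problems apply to it.

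Fourth, section 10.2.3 names neither watch and specifies no between-watch test or margin. The comparison is inferred from sections 6 and 7.4 and would be descriptive. That limits the consequence, but two rates reported under a comparative objective will be read side by side.

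Finally, sensor agreement is reported separately as bias, precision and A_RMS. Those are planned for the slow desaturation, restricted to stable reference values (section 10.1.2), so they do not settle what drives a difference in fast-event detection.

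**Conclusion.** The concern holds in conditional form. The visible text puts a continuous watch and a spot-checked watch under one all-events Detection Rate, with no stated definition of detection and no output showing events in which the Apple Watch was never checked. Unless Condition B guarantees a check inside every event, a difference between the two rates cannot be attributed to the sensors. Even with that guarantee, an unequal number of readings per event can favour the continuous device.

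For error-free sensors, the schedule-only gap could be anything from 0 points (checks timed to events, or events lasting at least T + m) to 100 points (events no longer than the reading window). At the assumed T = 60 s and m = 0 it is 67, 50, 25 and 0 points for events of 20, 30, 45 and 60 s. These figures illustrate sensitivity to the schedule; they do not estimate the bias in this trial. This is worth fixing before analysis, but it does not invalidate the planned rate.

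**What to change.** Keep the all-events Detection Rate as the as-used result, and add the following to section 10.2.

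1. Define a detected event for a watch: the threshold and the time window relative to the reference event. Unless the full Condition B text already does so, state when Apple checks are made.
2. Report the share of valid reference events with no Apple check attempted during the event.
3. Add a supplementary matched analysis. Restrict it to events with at least one Apple check attempted while the reference is in the event, take the W1 value at those check times, and score both watches with the same threshold. Show failed Apple checks separately. Fix in advance which instant of an Apple reading is matched and how readings that straddle the edge of an event are treated.
4. Give the W1-minus-Apple difference with a confidence interval from resampling whole subjects, because B-1 to B-3 can repeat within a subject.

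The matched analysis should sit beside the planned rate. Making it the only between-watch result would remove the W1's continuous reading from the comparison, which is a choice of estimand.

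The cost is SAP wording and one further analysis. The matched set will hold fewer events, so its interval will be wider. Apple check times must be logged; sections 3 and 8.4.1.1 describe manual entry in the data collection software, and whether usable times are kept needs to be confirmed.

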11.2. Source Documents

Source data is all information, original records of clinical findings, observations, or other activities in a clinical trial necessary for the reconstruction and evaluation of the trial. Source data are contained in source documents. Examples of these original documents and data records include: hospital records, clinical and office charts, laboratory notes, memoranda, recorded data from automated instruments, and copies or transcriptions certified after verification as being accurate and complete.

11.3. Case Report Forms

The site shall capture study data in case report forms (CRFs) for each subject enrolled, to be provided to the sponsor. CRFs may be in paper or electronic format through electronic data capture (EDC) software. Masimo shall ensure that systems used for electronic CRFs are compliant with the requirements of 21 CFR Part 11 and ISO / IEC 27001 certification. The CRFs will be completed and signed by the PI or delegate. This also applies to those subjects who fail to complete the study.

If a subject withdraws from the study, the reason must be noted on the CRF. The eCRFs are to be completed on an ongoing (weekly) basis. CRF entries and corrections will only be performed by study site staff, authorized by the investigator. For paper CRFs, entries and corrections to the CRF will be made following good documentation practices (GDP).

The CRF may include the following information, including but not limited to: inclusion/exclusion criteria, whether subject consent was obtained before start of study, demographic information, device readings, and if occurrence of any adverse event, protocol deviation, and device deficiencies, etc. The CRFs will be signed by the PI or delegate to attest that the data are complete and accurate.

CRF entries will be checked by the study monitor and any errors or inconsistencies will be queried to the site on an ongoing basis. Any changes made within an electronic CRF will be tracked by audit trail. Any changes on a paper CRF will be made directly on the CRF and will be initialed and dated by the person making the change. Query resolution will be assessed and confirmed by study monitor during site visit.

11.4. Data Transfer and Storage

Original paper CRFs will be stored in a secure location at the site. Copy of the original paper CRFs may be scanned and sent to sponsor. If using electronic CRFs, the site staff will be assigned unique usernames and passwords for data security. Final copies of the electronic CRFs in EDC are stored on a secure server.

Only authorized sponsor personnel will have access to study data, and will move it to a secure and backed-up drive at Masimo.

CRFs will be checked for completeness and if there are inconsistent or missing data points, queries will be generated. If delegated study staff are to correct the paper CRF, they shall follow GDP practices to strike through old entry, add in new entry, initial and date it, and provide the corrected information to sponsor. Corrections made to electronic CRFs will be tracked by audit trail and require PI or delegate sign-off.

11.5. Record Retention

Study data will be retained for the necessary period of time as required by the institution's regulations. Study records shall be retained for a minimum of two years after study closure. The institution's own retention policies and regulations may apply in addition to the minimal requirement.

12. AMENDMENTS TO THE CLINICAL INVESTIGATION PLAN

Any changes made to the clinical investigational plan/study protocol will be documented by way of an amendment. Before submitting a protocol amendment to the IRB, the protocol amendment must be agreed upon and signed by both the principal investigator and the sponsor. The protocol amendment will be submitted to the IRB for approval. At a minimum, a redline version and a clean version of the new protocol amendment will be kept on file by the PI and the sponsor. Protocol amendments will need

to be version controlled. Both PI and sponsor will retain the IRB approval letter as confirmation that the protocol amendment was approved.

13. DEVIATIONS FROM CLINICAL INVESTIGATION PLAN

Deviations from the protocol must receive both Sponsor and the investigator's IRB/ethics committee approval before they are initiated, with the exception that under emergency circumstances, deviations from the Clinical Investigation Plan to protect the rights, safety and well-being of human subjects may proceed without prior approval of the sponsor or the IRB/ethics committee.

Any protocol deviations initiated without Sponsor and the investigator's IRB/ethics committee approval that may affect the scientific soundness of the study, or affect the rights, safety, or welfare of study subjects, must be documented, and reported to the Sponsor and to the investigator's IRB/ethics committee as soon as a possible, but no later than 5 working days after the occurrence of the protocol deviation. In addition to documenting deviations on the CRF, the Protocol Deviation Form may also be used. If protocol deviations continue to occur frequently at a study site, a corrective and preventive action (CAPA) may be opened by the Sponsor.

Withdrawal of IRB approval: An investigator shall report to the sponsor a withdrawal of approval by the investigator's reviewing IRB as soon as possible, but no later than 5 working days of the IRB notification of withdrawal of approval.

14. DEVICE ACCOUNTABILITY

14.1. Receipt of Study Device

Upon receipt of the study device supplies, an inventory must be performed, and the device accountability log filled out and signed by the person accepting the shipment. It is important that the designated study staff counts and verifies that the shipment contains all the items noted in the shipment inventory. Any damaged or unusable study devices each shipment will be documented in the study files. The investigator must notify the study sponsor of any damaged or unusable study devices that were supplied to the investigator's site.

14.2. Use of Study Device

Use of device will be documented on case report forms for each subject. Any unused devices must be returned to the Sponsor at the end of the study or before the product's expiration date.

14.3. Return or Destruction of Study Device

At the completion of the study, there will be a final reconciliation of study devices shipped, devices used, and devices remaining. This reconciliation will be logged on the device accountability log. Any discrepancies noted will be investigated, resolved, and documented prior to the return or destruction of unused study devices. Devices destroyed on site will only be upon written instruction from the sponsor and will be documented in the study files. When a Masimo device deficiency is observed, every effort should be made to return the device and its packaging to the Sponsor in a timely manner.

15. STATEMENTS OF COMPLIANCE

This document is a clinical investigational plan for a human research study sponsored by Masimo Corporation. The study will be conducted in accordance with the ethical principles that have their origin in the Declaration of Helsinki. By participating in the study, the Investigator agrees to adhere to all stipulations of this protocol, the conditions of the Institutional Review Board (IRB) or Research Ethics Committee approval, federal and local regulatory requirements, 21 CFR 812, ISO-14155, International Conference on Harmonization Good Clinical Practice (ICH GCP) guidance.

The protocol, informed consent form(s), recruitment materials, and all participant materials will be submitted to the Institutional Review Board (IRB) for review and approval. Approval of both the protocol and the consent form must be obtained before any participant is enrolled. Any amendment to the protocol will require review and approval by the IRB before the changes are implemented to the study.

16. INFORMED CONSENT PROCESS

See subsection on [Informed Consent Process](#) under *Study Procedures*

17. ADVERSE EVENTS, ADVERSE DEVICE EFFECTS, AND DEVICE DEFICIENCIES

17.1. Definitions

The definitions for adverse event, adverse device effect, serious adverse event, serious health threat, serious adverse device effect, and unanticipated adverse device effect, device deficiencies are provided below (ISO 14155, 21 CFR 812.3(s)).

- **adverse event**: untoward medical occurrence, unintended disease or injury, or untoward clinical signs (including abnormal laboratory findings) in subjects, users, or other persons, whether related to the investigational medical device and whether anticipated or unanticipated (ISO 14155)
- **adverse device effect**: adverse event related to the use of an investigational medical device
- **serious adverse event**: adverse event that led to any of the following:
 - a) death
 - b) serious deterioration in the health of the subject, users, or other persons as defined by one or more of the following:
 - 1) a life-threatening illness or injury, or
 - 2) a permanent impairment of a body structure or a body function including chronic diseases, or
 - 3) in-patient or prolonged hospitalization, or
 - 4) medical or surgical intervention to prevent life-threatening illness or injury, or permanent impairment to a body structure or a body function,
 - c) fetal distress, fetal death, a congenital abnormality, or birth defect including physical or mental impairment

Note: Planned hospitalization for a pre-existing condition, or a procedure required by the Clinical Investigation Plan, without serious deterioration in health, is not considered a serious adverse event.

- **serious health threat**: signal from any adverse event or device deficiency that indicates an imminent risk of death or a serious deterioration in the health in subjects, users or other persons, and that requires prompt remedial action for other subjects, users or other persons.

Note: This would include events that are of significant and unexpected nature such that they become alarming as a potential serious health hazard or possibility of multiple deaths occurring at short intervals.

- **serious adverse device effect**: adverse device effect that has resulted in any of the consequences characteristic of a serious adverse event
- **unanticipated serious adverse device effect**: serious adverse device effect which by its nature, incidence, severity, or outcome has not been identified in the current risk assessment

Note: Anticipated serious adverse device effect (ASADE) is an effect which by its nature, incidence, severity, or outcome has been identified in the risk assessment.

- **device deficiency**: inadequacy of a medical device with respect to its identity, quality, durability, reliability, usability, safety, or performance

Note 1: Device deficiencies include malfunctions, use errors, and inadequacy in the information supplied by the manufacturer including labelling.

Note 2: This definition includes device deficiencies related to the investigational medical device or the comparator.

